Study population:	-To assess compliance of ESGO quality Indicators Patients with early-stage (FIGO stage I-II) EC that underwent surgical treatment with lymph node evaluation between January 2021 to December 2022, both included. A sample size of 1,032 patients may provide sufficient statistical power to evaluate the association between molecular subgroups and lymph node status. We assumed a 90% power for a 2-sided p-
Study population:	-To assess compliance of ESGO quality Indicators Patients with early-stage (FIGO stage I-II) EC that underwent surgical treatment with lymph node evaluation between January 2021 to December 2022, both included. A sample size of 1,032 patients may provide sufficient statistical power to evaluate the association between molecular subgroups and lymph node status. We assumed a 90% power for a 2-sided p-value of 0.05 and a minimum difference of 4.4 percentage points in

Inclusion criteria:	-Age 18 years or older		
	-Patient was operated during 2021-2022		
	-Histological confirmation of Endometrial Cancer with endometrioid		
	histology or high risk histology (serous, clear cell, carcinosarcoma		
	and mixed histologies)		
	-Preoperative FIGO stage I or II by MRI or US		
	-Preoperative CT-Scan or PET-CT without evidence of local or distant		
	disease (could be omitted in low-risk and intermediate		
	endometrial carcinoma with low grade histology)		
	-Surgical protocol according to ESGO/ESTRO/ESP guidelines		
	-A detailed sentinel lymph node study protocol must be accredite		
	either by ultra-staging or OSNA		
	-Molecular analysis performed on the pathology specimen		
	according to ESGO/ESTRO/ESP guidelines (POLE mutation analysis		
	could be omitted in low-risk and intermediate risk endometrial		
	carcinoma with low grade histology).		
Exclusion criteria:	-Pregnant women		
	-Previous hysterectomy		
	-Previous pelvic/para-aortic lymphadenectomy		
	-Presence of extra-uterine disease (peritoneal, visceral or suspicious		
	lymph node metastasis)		
	-Past medical history of any invasive tumor		
	-History of previous abdominal or pelvic radiotherapy of any type		
	(including braquitherapy)		
	-History of preoperative neoadjuvant chemotherapy		
Statistical	Quantitative data will be presented as mean and standard deviation		
considerations:	and qualitative variables with absolute values and percentages.		
	Additionally, qualitative variables among groups will be compared		

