4. OBJECTIVES

Primary objective

-To evaluate the lymph node involvement rate (sentinel) for each molecular subtype in patients with stage I/II EC.

Secondary objectives

- -To evaluate the lymph node involvement rate (sentinel and non-sentinel) for each prognostic risk group in patients with stage I/II EC.
- -To evaluate morbidity associated to SLN biopsy.
- -To assess compliance of ESGO quality Indicators.

We consider that our study will help to:

- ✓ Tailor the type of nodal staging depending on the molecular subgroup in early EC.
- ✓ Take a snapshot of the morbidity in SLN.
- ✓ Evaluate if the quality indicators described by ESGO are met.
- ✓ Know the degree of correlation between the molecular classification of the preoperative and the definitive biopsy.

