5. STUDY GENERAL DESIGN

STUDY GENERAL DESIGN

The study is a retrospective multicentric international observational study reviewing data of patients diagnosed with early-stage (FIGO stage I-II) EC and underwent surgical treatment with lymph node evaluation between January 2021 to December 2022, both included.

All data and records generated during this study will be kept confidential in accordance with Institutional policies and HIPAA on subject privacy. The Investigators and other site personnel will not use such data and records for any purpose other than conducting the study.

This protocol will be reviewed by the IRB of Clinica Universidad de Navarra, and the data collection will not start until the IRB approval is obtained. Each institution will be responsible of obtaining its own IRB/EC approval.

RECRUITMENT

A sample size of 1,032 patients may provide sufficient statistical power to evaluate the association between molecular subgroups and lymph node status. We assumed a 90% power for a 2-sided p-value of 0.05 and a minimum difference of 4.4 percentage points in prevalence rates of positive lymph nodes. We anticipated a potential dropout rate of 10%.

Gynaecological Cancer Centres/Units and hospitals regularly performing elective surgeries for EC internationally will be invited to participate in this study. Invitations will be sent through international/national and informal networks. Participating sites will register with the central audit team at Clinica Universidad de Navarra and will be provided with unique user access credentials for the database.

Each participating site (centre/unit/trust/hospital) will identify a principal investigator (PI) who will be responsible for coordinating data entry at their local site. The PI may have a bigger local reporting group/team with as many individuals as felt to be necessary to sustain the project. Team members may include gynaecological oncology trainees/fellows, medical/clinical oncologists, radiologists, pathologists, nurses, medical students, research staff, data managers. Each participating site will be provided a unique site code, individual username and password for database access. Inputting sites will only be able to access/see their own data and will not be able to see another site's data. The central coordinating centre team will be able to see individual data from all sites.

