7. EVALUATION

Definition of variables

Sentinel lymph node: Defined as the first echelon lymph node where the tumor directly

flows through the lymphatic duct.

Isolated tumor cells: <0.2mm or less than 200 tumoral cells in a single histologic section

Micrometastases: 0.2mm-0.2cm or more than 200 tumoral cells in a single histologic

section.

Macrometastases: Metastases >0.2cm

Data to be abstracted:

Medical history and demographic data will be reviewed. Patients will be grouped in

group 1 (POLEmut), group 2 (MMRd), group 3 (NSMP), group 4 (p53abn), depending on

the molecular profile. Preoperative FIGO stage, modality of initial treatment, final

pathology diagnosis, preoperative pathology analysis, type of surgery, perioperative

details and adverse events will be reviewed. Follow up until the date will be reviewed as

well. (Appendix).

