8. STATISTICAL ANALYSIS

Quantitative data will be presented as mean and standard deviation and qualitative

variables with absolute values and percentages. Additionally, qualitative variables

among groups will be compared by chi-square test or Fisher exact test; and quantitative

variables with t-test and ANOVA test. For the multivariate analysis a logistic regression model will be used.

Survival analysis will be performed using the Kaplan-Meier method and log-rank tests. Alpha error will be set at 5%.

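### Does the 90% power claim for a 4.4-point difference fail because it names no reference rate, subgroup sizes or contrast?

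*Combined protocol and SAP*

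**What the plan says.** The combined protocol and SAP, Section 5 (Recruitment), states: "A sample size of 1,032 patients may provide sufficient statistical power to evaluate the association between molecular subgroups and lymph node status". It assumes "90% power for a 2-sided p-value of 0.05 and a minimum difference of 4.4 percentage points in prevalence rates of positive lymph nodes" and adds "We anticipated a potential dropout rate of 10" per cent. The synopsis repeats the sample size, power and difference. Neither place says whether 1,032 already includes the allowance for dropout.

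The primary objective in Section 4 is "To evaluate the lymph node involvement rate (sentinel) for each molecular subtype in patients with stage I/II EC". Among the expected uses of the results, Section 4 lists: "Tailor the type of nodal staging depending on the molecular subgroup in early EC". Section 7 sorts patients into "group 1 (POLEmut), group 2 (MMRd), group 3 (NSMP), group 4 (p53abn), depending on" the molecular profile. Section 8 says that qualitative variables "among groups will be compared by chi-square test or Fisher exact test", and adds a logistic model for multivariable work. It names no pairwise contrast and no powered test.

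**The concern.** A sample size for a difference in proportions depends on the base rate and on the group sizes, and neither is given. The power is attached to an association across four subgroups, yet a single 4.4-point difference describes two groups. A test on 3 degrees of freedom needs more information than a two-group test to reach the same power.

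If the 90% came from a two-group calculation and was then read as applying to the four-group test, a non-significant result could be taken as stronger evidence of similar nodal risk than it is. That would matter to a reader who wants to adapt nodal staging by subgroup.

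**Working it through.** **Inputs from the plan.** N = 1,032, power 90%, two-sided alpha 0.05, difference d = 0.044, dropout 10% (Section 5); four groups (Section 7). If 1,032 includes the dropout allowance, 1,032 x 0.9 = 928.8, about 929 evaluable. The lower rate and the subgroup sizes are not given, so every value used for them below is an assumption.

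**1. Can 1,032 be reproduced?** For two equal groups with pooled variance under the null, n per group = [1.960 x sqrt(2 x pbar x (1 - pbar)) + 1.2816 x sqrt(p1(1 - p1) + p2(1 - p2))]^2 / d^2.

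With p1 = 0.023, p2 = 0.067 and pbar = 0.045:

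- first term: 1.960 x sqrt(0.08595) = 0.5746
- second term: 1.2816 x sqrt(0.08498) = 0.3736
- n = 0.9482^2 / 0.001936 = 464.4 per group
- total 928.8, and 928.8 / 0.9 = 1,032

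Other lower rates give other totals after the dropout allowance: 1,010 at 2.2%, 1,054 at 2.4% and 1,607 at 5%. With no allowance added, 2.8% v 7.2% gives about 1,028. The figure is therefore consistent with a two-group calculation at a lower rate of roughly 2 to 3%. This does not prove that it was obtained that way.

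**2. Four-group chi-square if 4.4 points is the widest gap.** For a fixed range, power is greatest when each subgroup sits at the lower or the upper rate. With a share f of patients at the upper rate, the noncentrality is N x f(1 - f) x d^2 / [pbar(1 - pbar)], and 90% power on 3 df needs 14.17.

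At a lower rate of 2% the best share is f = 0.365, so pbar = 0.02 + 0.365 x 0.044 = 0.0361:

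- N = 929: 929 x 0.2318 x 0.001936 / 0.0348 = 12.0, power 84.0%
- N = 1,032: 13.3, power 87.9%

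These are large-sample values. Simulating many subgroup mixes and high/low patterns gives slightly higher maxima:

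| Lower rate | Best found, 929 | Best found, 1,032 | Four equal groups, 929: two high, two low | Four equal groups, 929: rates evenly spread |
|---|---|---|---|---|
| 1.5% | 91.3% | not needed | not needed | not needed |
| 2% | 86.5% | about 90% | 83% | 54% |
| 2.3% | 83.7% | about 87% | 80% | 50% |
| 5% | 61.8% | not tabulated | 57% | 33% |

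**3. Readings under which 90% holds.** These use 929 evaluable patients and an assumed mix of 65, 260, 446 and 158.

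- *Neighbouring subgroups 4.4 points apart* (for example 2.0, 6.4, 10.8 and 15.2%). The lowest four-group power over all orderings is 91.4% at a lower rate of 2%, 90.3% at 2.3% and 80.6% at 5%.
- *Two-group contrast, largest subgroup v the rest* (446 v 483). Power is 93% at 2%, 91% at 2.3% and 75% at 5%.

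**4. Precision for the stated objective.** In the same assumed mix, with 5% involvement, Wilson 95% intervals are 1.8 to 13.2% (n = 65), 2.5 to 9.6% (n = 158), 2.9 to 8.4% (n = 260) and 3.3 to 7.4% (n = 446). The patients included fix these widths, whatever the power sentence says.

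**The case for a change.** The strongest case for a change is that the omission is real, lies in intact text, and affects what the 90% means. Section 5 ties the power to the molecular subgroups as a set, Section 8 compares across groups, and the only reconstruction that fits is a two-group one. With rates spread evenly over 4.4 points in four equal groups, power would be 54% at a lower rate of 2% and 33% at 5%. The remedy would be a few sentences.

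The omission stands: a reader cannot check the figure or tell which comparison it covers. The shortfall does not follow from the documents. It treats a minimum difference of interest as a ceiling on the gap between any two of four groups. That is a conventional worst case for a multi-group test, but the plan does not state it. It needs a lower rate that the plan never gives. It also takes 1,032 as already inflated for dropout, which is the likelier reading but is not stated. Finally, the four-group test is never named as the powered test. Section 8 is a general sentence, and its logistic model can carry two-group contrasts.

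**Conclusion.** No change is called for. The basis of the power figure is not written down, but 1,032 is not shown to be wrong, and it matches a sound two-group calculation at 2.3% v 6.7%.

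Under all three conditions (4.4 points the widest gap, about 929 evaluable, lower rate about 2% or more), even the most favourable four-group configuration found falls short of 90%. The gap is 90 - 86.5 = 3.5 points at a lower rate of 2%, 6.3 points at 2.3% and 28.2 points at 5%. It is larger for less favourable subgroup sizes and rate patterns. It disappears at a lower rate of about 1.5%, is negligible at 2% if all 1,032 are analysed, and is absent at 2 to 2.3% for the two-group and neighbouring-step readings in the working.

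The practical consequence is limited. The study is retrospective, its primary objective is a rate for each subtype, Section 5 says only that the number may suffice, and no rule turns a non-significant test into a decision. Analysts would ordinarily report each subgroup rate with a confidence interval, which shows directly how much a null comparison can support. Writing down the missing assumptions would need the sponsor's own inputs and would leave the patients, analyses and results as they are. The 90% should simply not be read as a guarantee for the four-group test.

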6. STUDY POPULATION

INCLUSION CRITERIA

A patient will be considered eligible for inclusion in this study if all the following criteria are met:

- -Age 18 years or older
- -Patient was operated during 2021-2022
- -Histological confirmation of Endometrial Cancer with endometrioid histology or high risk histology (serous, clear cell, carcinosarcoma and mixed histologies)
- -Preoperative FIGO stage I or II by MRI or US
- -Preoperative CT-Scan or PET-CT without evidence of local or distant disease (could be omitted in low-risk and intermediate risk endometrial carcinoma with low grade histology)
- -Surgical protocol according to ESGO/ESTRO/ESP guidelines
- -A detailed sentinel lymph node study protocol must be accredited, either by ultrastaging or OSNA
- -Molecular analysis performed on the pathology specimen according to ESGO/ESTRO/ESP guidelines (POLE mutation analysis could be omitted in low-risk and intermediate risk endometrial carcinoma with low grade histology).

EXCLUSION CRITERIA

-Pregnant women

-Previous hysterectomy

-Previous pelvic/para-aortic lymphadenectomy

-Presence of extra-uterine disease (peritoneal, visceral or suspicious lymph node

metastasis)

-Past medical history of any invasive tumor

-History of previous abdominal or pelvic radiotherapy of any type (including

braquitherapy)

-History of preoperative neoadjuvant chemotherapy

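### ESGO quality-indicator compliance is assessed in a sample selected partly on conformity of care, so any indicator fixed by an entry condition is met by eligibility and is not evidence of compliance

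*Combined protocol and SAP*

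**What the plan says.** Section 4 (Objectives) lists among the secondary objectives "To assess compliance of ESGO quality Indicators", and adds that the study will help to "Evaluate if the quality indicators described by ESGO are met". The synopsis repeats the objective.

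Section 5 (Study general design) limits the review to patients who "underwent surgical treatment with lymph node evaluation between January 2021 to December 2022, both included". On recruitment it says: "Gynaecological Cancer Centres/Units and hospitals regularly performing elective surgeries for EC internationally will be invited to participate in this study".

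Section 6 (Study population) makes the entry criteria cumulative: "A patient will be considered eligible for inclusion in this study if all the following criteria are met". Three of them concern the standard of care:

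- "Surgical protocol according to ESGO/ESTRO/ESP guidelines"
- "A detailed sentinel lymph node study protocol must be accredited, either by ultrastaging or OSNA"
- molecular testing of the specimen in line with the same guidelines, where POLE testing may be left out in low- and intermediate-risk tumours of low grade.

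Section 8 (Statistical analysis) contains nothing specific to compliance. Its general rule is to present qualitative "variables with absolute values and percentages".

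**The concern.** The same kind of fact, whether care conformed to a standard, serves both as a condition of entry and as something to be measured. Where an entry condition determines an indicator, every patient in the denominator is also in the numerator. The resulting percentage describes who was admitted, not how often the standard was followed. Section 4 would nevertheless have it read as showing that the indicator is met.

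What is at stake is one secondary conclusion. The primary objective, sentinel-node involvement by molecular subtype, does not depend on it. The entry criteria suit that objective, because it needs both a molecular class and a detailed nodal work-up.

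**Working it through.** **Figure in the plan.** The plan gives no figure for compliance. The sample size of 1,032 in Section 5 was set for the association between molecular subgroup and nodal status and does not bear on this point, so there is nothing to reproduce.

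**Count of conditions.** Section 6 has 8 inclusion criteria, of which 3 require care to follow a stated standard (surgical protocol, sentinel-node protocol, molecular analysis). Section 5 adds 1 (nodal evaluation). That makes 3 + 1 = 4 conditions. The imaging criteria are framed as findings on disease extent and are not counted.

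**Level at which each applies.**

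- *Nodal evaluation (Section 5):* patient-level, because it describes what the patient underwent.
- *Molecular analysis (Section 6):* patient-level, because it refers to the patient's specimen. The POLE exception means that complete molecular classification is not fixed in the low-grade, low- and intermediate-risk cases.
- *Surgical protocol (Section 6):* the list is one of patient eligibility criteria, which favours a per-patient reading. The word protocol also allows a per-site one.
- *Sentinel-node protocol (Section 6):* the same ambiguity. Accreditation of a protocol reads readily as a property of the centre.

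So 2 conditions are patient-level by wording and 2 are open.

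**Effect on a reported percentage.** Let c be compliance with an indicator among all operated patients who meet the other criteria. Let e be the share of non-compliant patients that the entry condition removes, with all compliant patients kept. Then

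observed compliance = c / [c + (1 − c)(1 − e)].

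- *Indicator fully determined by a patient-level condition, e = 1:* c / c = 100% for any c above zero. For example, 1,032 eligible patients could come from 1,032 / 0.9 ≈ 1,147 operated patients at c = 90%, or from 1,032 / 0.5 = 2,064 at c = 50%. Both would report 100%.
- *Indicator unrelated to entry, e = 0:* observed compliance equals c, and the percentage is informative for this sample.
- *Partial selection, as under a per-site reading, e between 0 and 1:* observed compliance is above c but can still vary. With e = 0.5:
  - c = 0.5 gives 0.5 / 0.75 = 67%
  - c = 0.7 gives 0.7 / 0.85 = 82%
  - c = 0.9 gives 0.9 / 0.95 = 95%

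The values of c and e are assumptions chosen to show the mechanism. The documents supply neither, so these are not estimates for this study.

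**The case against.** The strongest reply is that the claim is conditional. Without the list of indicators, no single one can be shown to coincide with an entry condition, and the affected set could be empty. That stands, and it is why no number of indicators and no size is claimed. It does not remove the point. Conformity with ESGO/ESTRO/ESP guidance is required for entry while ESGO indicators are the outcome, so overlap has to be checked before any percentage is read as compliance.

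A second reply is that the patient-level conditions are narrow. Having had nodal evaluation does not settle how it was done, whether mapping succeeded or what morbidity followed. That also stands, and indicators on such matters remain assessable here.

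A reader might be tempted by four stronger readings, none of which the documents support:

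- *Every included patient had guideline-conform surgery and sentinel-node work-up, so the whole objective is empty.* The two criteria speak of a protocol and may apply per site. Individual compliance could then differ.
- *Compliance will be overstated by some stated amount.* No inputs for such a figure are given.
- *The plan claims compliance in routine practice at large.* Section 4 speaks of assessing compliance and of indicators being met. It does not extend the result beyond the study patients, and describing compliance among them is a legitimate aim.
- *The plan fails to define its indicators.* Section 7 (Evaluation) refers to an appendix for the data to be abstracted, and no data list is visible in the text available. Nothing can be charged to the plan on that account.

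**Conclusion.** The concern holds in limited form and is minor. Any indicator determined by nodal evaluation or by guideline-conform molecular analysis is met by eligibility, subject to the POLE exception, and its percentage is not evidence of compliance. The surgical-protocol and sentinel-node-protocol criteria have the same effect if applied to each patient. If applied to each site, compliance can vary but is favoured by selection, on the assumption that centres with such a protocol comply better than centres without one.

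The direction is upward or neutral. The number of indicators affected and the size of the effect are unknown. Section 8 has no step that would separate fixed indicators from informative ones. The primary objective and the remaining indicators are not affected.

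**What to change.** Reword the Section 4 objective, for example: *To describe, in eligible patients at participating centres, compliance with the ESGO quality indicators that are not determined by the eligibility criteria.* In the report, show any indicator fixed by an entry criterion as not assessable rather than as met, and flag those favoured by selection. Sorting them requires the sponsor to settle whether the two protocol criteria were applied per patient or per site.

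The cost is wording only, with no new data and no change to eligibility or to the primary analysis. The downside is that fewer indicators can be interpreted, and the conclusion does not extend beyond eligible patients at participating centres.

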3. BACKGROUND

The management of endometrial cancer (EC) is currently undergoing a true revolution in terms of diagnosis and treatment. Since 2013 and thanks to the TCGA project¹ (The Cancer Genome Atlas), four distinct molecular subgroups (POLE, MMR-D, Copy number low, Copy number high) with distinct prognostic implications were identified.

Subsequently, PROMISE study² brought this "new era" closer to daily clinical practice. These new findings led ESGO³ (European Society of Gynecologic Oncology) to decide to integrate this molecular classification into the definition of the different risk groups.

Currently, thanks to the retrospective analysis of the PORTEC-3 cohort^{4,5}, we know that these four molecular subgroups may present differences in survival in high-risk patients depending on the type of treatment proposed, chemoradiotherapy vs. adjuvant radiotherapy. This question will be answered by the RAINBO trial⁶ (Refining Adjuvant treatment IN endometrial cancer Based On molecular profile).

On the other hand, the surgical management of early endometrial cancer (stage I/II) has been changing for some years now, especially with regard to nodal staging, from modulation of treatment depending on the risk group (pelvic lymphadenectomy +/-sentinel lymph node (SLN) for low and intermediate risk groups vs. aortopelvic lymphadenectomy +/- SLN for those at high risk) to a generalization of treatment based on detailed study of the sentinel node following the algorithm described by the group of Abu-Rustum NR et al⁷.

Just as the RAINBO study will try to clarify the type of adjuvant treatment necessary for each molecular subgroup, we do not currently know if it could be possible to tailor the type of lymph node staging in early EC (the most common and most frequent in our daily clinical practice) depending on the molecular subgroup^{8,9}.

We therefore propose a study to evaluate the lymph node involvement rate depending on the molecular subgroup in early-stage EC (I/II).

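### Low-grade, lower-risk patients may go without POLE testing, but the four-group analysis does not separate them, so the POLEmut node rate can be biased where testing was omitted

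*Combined protocol and SAP*

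**What the plan says.** The primary objective (section 4) is "To evaluate the lymph node involvement rate (sentinel) for each molecular subtype in patients with stage I/II EC". Section 4 adds that the result should help to tailor nodal staging by molecular subgroup.

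Section 6 requires molecular analysis according to the European guidelines, with an exception: "POLE mutation analysis could be omitted in low-risk and intermediate risk endometrial carcinoma with low grade histology". The synopsis has the same exception ("could be omitted in low-risk and intermediate risk endometrial"). Patients who use it remain eligible.

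Section 7 assigns patients to "group 1 (POLEmut), group 2 (MMRd), group 3 (NSMP), group 4 (p53abn), depending on" the molecular profile. There is no category for POLE not tested and no assignment rule for such patients.

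Section 8 lists descriptive statistics, chi-square or Fisher tests, t-test and ANOVA, and survival methods. On modelling it says only "For the multivariate analysis a logistic regression model will be used", and it names no covariates. It mentions neither a stratified analysis nor one restricted to tested patients.

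A secondary objective is "To evaluate the lymph node involvement rate (sentinel and non-sentinel) for each prognostic risk group in patients with stage I/II EC". This gives rates by risk group, not by molecular group within risk group.

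**The concern.** A patient can be called POLEmut only if POLE was tested. The permission to omit the test depends on grade and risk, features plausibly related to node status. Where it was used, the POLEmut group in the analysis is therefore a selected subset of the POLEmut tumours in the cohort: those outside the exempt stratum, plus exempt patients who happened to be tested.

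On the natural reading, untested patients are grouped by their remaining markers. Their POLEmut cases then sit unseen in other groups. No labelling convention brings them back, and a larger sample does not remove the bias.

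At stake is one of the four rates in the primary objective. Without the number untested, a reader of the results could not judge how far that rate is affected.

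**Working it through.** **The plan's own figures.** The documents give no figure for this bias: no testing frequency, no POLEmut prevalence and no node rate by group. From section 5 come the sample size of 1,032, the 10% dropout and the 4.4-point design difference. The check uses 1,032 × 0.90 = 929 evaluable patients. It does not depend on whether 1,032 is right, which cannot be confirmed because no base rate or pair of groups is stated.

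**Assumed inputs (none is in the documents).**
- L, share of the cohort in the exempt stratum: 50–70%.
- o, share of exempt patients not tested: varied up to 100%.
- a and b, POLEmut node rates inside and outside the exempt stratum: from 3% v 5% to 2% v 12%.
- POLEmut prevalence: 7%, equal in both strata.

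**Formula.** With equal prevalence:
- true rate = La + (1−L)b
- labelled rate = [L(1−o)a + (1−L)b] / (1−Lo)
- bias = labelled − true = (b−a) × k, with k = L(1−L)o / (1−Lo)

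**Results (percentage points).**

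| o | k at L = 0.5 / 0.6 / 0.7 | 3% v 5% | 2% v 12% |
|---|---|---|---|
| 25% | 0.071 / 0.071 / 0.064 | 0.1 | 0.6–0.7 |
| 50% | 0.167 / 0.171 / 0.162 | 0.3 | 1.6–1.7 |
| 75% | 0.300 / 0.327 / 0.332 | 0.6–0.7 | 3.0–3.3 |
| 100% | 0.50 / 0.60 / 0.70 | 1.0–1.4 | 5.0–7.0 |

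Two worked cases:
- L = 0.6, o = 0.5, 3% v 5%: true rate 0.6×3 + 0.4×5 = 3.8%; labelled rate (0.3×3 + 0.4×5)/0.7 = 4.1%.
- L = 0.7, o = 1, 2% v 12%: true rate 0.7×2 + 0.3×12 = 5.0%; labelled rate 12.0%.

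If a = b, the bias is zero. If a exceeds b, the sign reverses.

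**Unequal prevalence.** If POLEmut prevalence outside the stratum is half to double that inside, k is 0.12–0.17 at o = 50% and 0.33–0.82 at o = 100%.

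**When does the bias reach 4.4 points?** With gap g = b−a in points, solving g × k = 4.4 gives o = 4.4 / [gL(1−L) + 4.4L].
- g = 10, L = 0.7: 4.4/5.18 = 85%
- g = 9, L = 0.7: 4.4/4.97 = 89%
- g = 10, L = 0.5: 4.4/4.70 = 94%
- g = 7, L = 0.7: 4.4/4.55 = 97%
- g = 5, L = 0.7: 4.4/4.13 is above 100%, so it is not reached

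About 85% is therefore the minimum omission over the gaps considered, and most combinations need more or never get there.

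**Numbers of patients.** 929 × 0.07 = 65 POLEmut cases, of which 33–46 are exempt and 20–33 testing-required. At 50% omission about 16–23 go unlabelled; at 100%, 33–46.

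**Effect on NSMP.** Suppose all missed cases are labelled NSMP. The NSMP rate falls by (n−a)m/(s+m), where m = 0.07Lo, s is the NSMP share (assumed 40–60%), n its node rate (assumed 4–10%) and a = 2–3%. At 100% omission the smallest fall is (4−3) × 0.035/0.635 = 0.06 points and the largest (10−2) × 0.049/0.449 = 0.87. At 50% the range is 0.03–0.46.

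**The case against.** **The labelling rule may exist elsewhere.** Section 6 defers to guidelines whose text is not in the documents, and the data-item list that section 7 calls the Appendix is not visible. Either might say how untested tumours are labelled. This stands, and the point does not claim that a labelling rule is absent everywhere. A label would still not identify untested POLEmut cases, and section 8 would still not separate them.

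**The estimand may be narrower.** The labelled rate correctly describes patients whose POLE status was known, and one could argue that only they could have staging tailored to a POLE result. This stands in part: the bias exists only if the target is all POLEmut tumours in the cohort. Section 4 states its objective for each subtype in stage I/II disease without restricting it to tested patients, so the wider reading is reasonable, and the plan should say which is meant.

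**The size is assumed and often small next to sampling error.** This stands. With 3 events in 65 POLEmut patients the exact 95% interval is 1.0–12.9%, far wider than a 1.7-point bias.

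**Stronger readings the documents do not support.** A reader might infer that untested patients are dropped. Section 6 makes them eligible and section 7 groups patients, so nothing supports that. A reader might also infer that the POLEmut rate will be inflated, or that the bias will rival the 4.4-point design difference. The documents give neither the direction nor the omission frequency, and 4.4 points needs at least about 85% omission even at a 10-point gap. Nor is this a criticism of the testing permission itself, on which no view is taken.

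**Conclusion.** The concern holds in a conditional form. As an estimate for all POLEmut tumours in the cohort, the labelled POLEmut node rate is biased if two things are true: POLE testing was omitted in some exempt patients, and the POLEmut node rate differs between the exempt stratum and the rest. The documents settle neither.

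The sizes worked out above rest wholly on assumed inputs. They range from negligible at low omission or a small gap to several points only when nearly all exempt patients went untested and the gap is wide. The other groups are little affected, with NSMP moving by under 1 point. The primary four-group display is not invalidated. What is missing is an analysis that shows whether the POLEmut figure can be taken as a cohort-wide rate. This is a cheap improvement, not a fatal flaw.

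**What to change.** **Section 7.** Record POLE as tested or not tested, and flag untested patients together with their MMR and p53 results.

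**Section 8.** Keep the pooled four-group table as the main display of the primary objective, report the number untested, and add:
- (a) The POLEmut node rate and its comparison with the other groups among POLE-tested patients only. The POLEmut figure itself does not change, since every labelled case was tested; the gain is that the comparison groups come from the same tested population.
- (b) Node rates by molecular group within the exempt and testing-required strata.

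Build the strata from preoperative stage, grade and histology only. Final stage can include nodal status, which is the outcome. Risk groups cannot be used directly, because section 3 reports the decision to "integrate this molecular classification into the definition of the different risk groups". State that the strata approximate the exemption in section 6.

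If few or no exempt patients were tested, say that the POLEmut rate applies to the testing-required stratum only.

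**Cost.** At most one data field, one table and some wording. Section 7 already abstracts preoperative FIGO stage and "pathology diagnosis, preoperative pathology analysis, type of surgery, perioperative" details, which should be enough to build the strata. The downside is imprecision: with about 20–33 testing-required POLEmut patients on the assumptions above, the exact 95% interval is 1–32% for 2/20 and 2–24% for 3/33. For that reason an adjusted model for this comparison is not recommended; with so few events it would be barely estimable.
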